3. STUDY DESIGN AND METHODOLOGY

This is a postmarketing, open-label, 5-period crossover drug interaction study designed to evaluate the potential effects of coadministration of 4 different phosphate binders on the PK of orally administered TPOXX in healthy adult subjects. A total of 44 subjects, ages 18 to 50, inclusive, will be enrolled and be randomly assigned to 1 of 4 treatment sequences. The study will consist of a screening period (Day –28 to Day –2), 5 treatment periods (Day –1 to Day 31), an end-of-study visit (Day 36 [+2 days]), and a follow-up telephone call (Day 59 [+4 days]). The treatment sequences and periods will be as follows:

Treatment Sequence	Period 1 Treatment	Period 2 Treatment	Period 3 Treatment	Period 4 Treatment	Period 5 Treatment
ABCDE	A	В	С	D	Е
ACEBD	A	С	Е	В	D
ADBEC	A	D	В	Е	С
AEDCB	A	Е	D	С	В

- Treatment A: A single oral dose of 600 mg (3×200 mg capsules) TPOXX.
- Treatment B: A single oral dose of 600 mg (3 × 200 mg capsules) TPOXX coadministered with a single oral dose of 1600 mg (2 × 800 mg tablets) sevelamer carbonate (Renvela® or generic equivalent).
- Treatment C: A single oral dose of 600 mg (3 × 200 mg capsules) TPOXX coadministered with a single oral dose of 500 mg sucroferric oxyhydroxide (Velphoro®) chewable tablet.

- Treatment D: A single oral dose of 600 mg (3 × 200 mg capsules) TPOXX coadministered with a single oral dose of 1334 mg (2 × 667 mg capsules) calcium acetate (PhosLo® generic equivalent).
- Treatment E: A single oral dose of 600 mg (3 × 200 mg capsules) TPOXX coadministered with a single oral dose of 500 mg lanthanum carbonate (Fosrenol® or generic equivalent) chewable tablet.

There will be a washout period of 7 days between dosing in each treatment period. All subjects will be provided a meal (consisting of approximately 600 calories and 25 g fat). The meal should be completed within 30 minutes. Subjects should be administered study drug as soon as possible following completion of the meal but no more than 30 minutes should elapse between meal completion and study drug administration. Study drug and meals must be taken with water only, and no other beverage except water should be ingested within 3 hours before or 3 hours after study drug administration. Water is allowed at all times throughout the study. Subjects must fast for 2 hours after taking study drug as further food consumption may affect drug absorption.

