6.2.5 Electrocardiograms

A 12-lead ECG will be obtained after the subject has been in a supine position for at least 10 minutes at the time points indicated in the schedule of events (Table 9-1 and Table 9-2).

On Day 1 of each period, an ECG will be recorded 4 hours after study drug administration. The acceptable window for collection from the scheduled collection time point is ± 15 minutes.

Electrocardiogram assessments will include comments on whether the tracings are normal or abnormal, rhythm, presence of arrhythmia or conduction defects, morphology, any evidence of myocardial infarction, or ST-segment, T-wave, and U-wave abnormalities. In addition, measurements of the following intervals will be measured and reported: heart rate; PR, RR, and QT interval; QTcF, QT interval corrected using Fridericia's formula; and QRS duration. All ECGs must be performed by an experienced ECG technician.

The investigator will determine whether any of the 12-lead ECG results are clinically significant or not clinically significant.

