7.3.2 Safety Analyses

Adverse events will be coded by preferred term and system organ class using the latest version of the Medical Dictionary for Regulatory Activities and summarized by treatment and overall. All AE data will be presented in a data listing. Treatment-emergent AEs will be summarized by treatment and overall, as well as by severity and relationship to study drug. Serious AEs and AEs leading to discontinuation of study drug will also be presented in the data listings and summarized by treatment and overall.

Actual values and changes from baseline for clinical laboratory test results, vital sign measurements, and 12-lead ECG results will be summarized by treatment at each time point using descriptive statistics (number of subjects, mean, SD, minimum, median, and maximum). Shift tables will be generated for clinical laboratory test results. Physical examination findings will be presented in a data listing.

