General study descriptors, as in subject disposition, demographics, protocol deviations, and enrollment characteristics, will be summarized for all randomized subjects, regardless of treatment sequence. Otherwise, safety outcomes, as in adverse events, lab values, vital signs, and electrocardiogram measures, will be summarized by treatment. The treatments below will be used for such presentation:

- TPOXX
- TPOXX + Sevelamer Carbonate
- TPOXX + Sucroferric Oxyhydroxide
- TPOXX + Calcium Acetate
- TPOXX + Lanthanum Carbonate

All data listings will be sorted by treatment and subject number.

No algorithm for imputation of missing data will be employed. Missing data will be treated as missing. If partial data exists for concomitant medications, the start dates will be imputed to the first of the month (for missing day) or first of the year (for missing day and month) for purposes of assigning a prior mediation flag.

There are no plans to derive visit windows; visits will be used in the analyses as reported on the eCRF.

Study days are calculated with respect to the first dose date as below:

- If the assessment/observation date is on or after the first dose date, then Study Day = Assessment/Observation Date First Dose Date + 1;
- Otherwise, Study Day = Assessment/Observation Date First Dose Date

Baseline will be defined as the day the subject checks in (Day -1) before the first dose of study drug administration, unless otherwise specified.

For summary of safety assessments, if there are repeated measurements at a time point, the first non-missing assessment at that time point will be used in the summary tables.

Unscheduled results will not be included in the summary tables, except for determining Baseline, but will be presented in data listings.

The methodology and data handling specifications for PK data are detailed in Section 8.

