9.5 Electrocardiograms

Single 12-lead ECGs will be obtained after the subject has been in the supine position for at least 10 minutes. A single repeat measurement is permitted at screening for eligibility determination. Electrocardiogram assessments will include comments on whether the tracings are normal or abnormal, rhythm, presence of arrhythmia or conduction defects, morphology, any evidence of myocardial infarction, or ST-segment, T-wave, and U-wave abnormalities.

In addition, measurements of the following intervals will be measured and reported: heart rate; PR, RR, and QT interval; QTcF, QT interval corrected using Fridericia's formula; and QRS duration. All ECGs must be performed by an experienced ECG technician.

Draft Statistical Analysis Plan, Version **2.0**Date Issued: 8OCT2022

SIGA Technologies, Inc. Protocol: SIGA-246-023

Single 12-lead ECG will be performed at the timepoints indicated in the schedule of assessments (schedules of assessments can be found in Section 13).

Actual values at baseline for numeric ECG data will be summarized by visit and treatment for subjects in the safety population.

All ECG data will be presented in a data listing.

10. Interim Analysis

No formal interim analyses will be performed in this study.

11. Changes in the Planned Analysis

Any changes from this statistical analysis plan will be documented in the CSR for this study.

SIGA Technologies, Inc.

Protocol: SIGA-246-023

Draft Statistical Analysis Plan, Version 2.0

Date Issued: 8OCT2022

12. References

- 2. Department of Health and Human Services (DHHS), Food and Drug Administration, Center for Drug Evaluation and Research, Center for Drug Evaluation and Research. Guidance for Industry: Clinical Drug Interaction Studies—Cytochrome P450 Enzyme-and Transporter-Mediated Dug Interactions. January 2020 [cited 24 Jan 2022]. Available from: https://www.fda.gov/media/134581/download.
- 3. Division of AIDS (DAIDS), National Institute of Allergy and Infectious Diseases, National Institutes of Health, US Department of Health and Human Services. Division of AIDS (DAIDS) table for grading the severity of adult and pediatric adverse events. July 2017 [cited 2020 Aug 18]. Available from:
 - https://rsc.niaid.nih.gov/sites/default/files/daidsgradingcorrectedv21.pdf.

13. Schedule of Events

Schedule of Events: Period 1 through Period 3

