- (d) Vital sign measurements included systolic and diastolic blood pressures, heart rate, respiratory rate, and body temperature. Vital signs were measured at screening, and in each period, on Day –1; within 60 minutes prior to dosing; and at 4, 8, 12, 24, and 48 hours following dosing in each period after the subject has been in a seated position for at least 5 minutes.
- (e) Fasting lipid panel included cholesterol (total, high-density lipoprotein, calculated low-density lipoprotein, and triglycerides).
- (f) Clinical laboratory testing included hematology and serum chemistry.
- (g) Clinical laboratory testing at screening included hematology, serum chemistry, and urinalysis.
- (h) For postmenopausal women, a serum follicle-stimulating hormone test was performed at screening.
- (i) Women of childbearing potential only.
- (included alcohol, cotinine, amphetamines (including methamphetamines and ecstasy/methylenedioxymethamphetamine), barbiturates, benzodiazepines, cannabinoids (including tetrahydrocannabinol), cocaine metabolites, and opiates (including heroin, codeine, and oxycodone). A urine drug screen including alcohol and cotinine was collected and sent to the central laboratory at the screening visit. A urine drug screen and alcohol breath test using a breathalyzer was performed and read locally on Day –1.
- (k) Randomization occurred according to the randomization schedule before study drug administration on Day 1 of Period 1 after it has been confirmed that the subject fulfilled all eligibility criteria. Subjects were randomly assigned to receive study drug in 1 of 4 treatment sequences (ABCDE, ACEBD, ADBEC, and AEDCB) in 1:1:1:1 ratio.
- (1) A single 12-lead ECG was obtained after the subject had been in the supine position for at least 10 minutes. On Day 1 of each period, an ECG was recorded 4 hours after study drug administration. The acceptable window for collection from the scheduled collection time point was ±15 minutes.

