Table 14.2.3.2	Non-Parametric Statistical Analysis of TPOXX	PK Population
Table 14.3.1.1	Overall Summary of Adverse Events	Safety Population
Table 14.3.1.2	Adverse Events by System Organ Class and Preferred	Safety Population
	Term	
Table 14.3.1.3	Serious Adverse Events by System Organ Class and	Safety Population
	Preferred Term	
Table 14.3.1.4	Adverse Events by Relationship to Study Drug	Safety Population
Table 14.3.1.5		Safety Population
Table	Summary and Change from Baseline in Hematology	Safety Population
14.3.4.1.1		
Table	Shift from Baseline in Hematology	Safety Population
14.3.4.1.2		
Table	Summary and Change from Baseline in Chemistry	Safety Population
14.3.4.2.1		
Table	Shift from Baseline in Chemistry	Safety Population
14.3.4.2.2		
Table	Summary and Change from Baseline in Urinalysis	Safety Population
14.3.4.3.1		
Table	Shift from Baseline in Urinalysis	Safety Population
14.3.4.3.2		
Table 14.3.5	Summary and Change from Baseline in Vital Signs	Safety Population
	Measurements	

Table 14.3.6	Summary and Change from Baseline in Electrocardiogram	Safety Population
	Measurements	
Figure 14.2.1	Mean Plasma Concentration versus Time Profiles for	PK Population
	TPOXX	
Figure 14.2.2	Individual Plasma Concentration versus Time Profiles	Safety Population
	for TPOXX	
Figure 14.2.3	Forest Plot to Assess the Relative Bioavailability of	PK Population
	TPOXX	

15. Index of Listings

Listing Number	Name							
Listing 16.1.7	andomization							
Listing 16.2.1	Subject Disposition							
Listing 16.2.2	Protocol Deviations							
Listing 16.2.3	Subjects Excluded From Analysis Populations							
Listing 16.2.4.1	Demographic and Baseline Characteristics							
Listing 16.2.4.2	Medical History							
Listing 16.2.4.3	Prior and Concomitant Medication							
Listing 16.2.4.4	Medical or Surgical Treatment Procedures							
Listing 16.2.5	Study Drug Administration							
Listing 16.2.6.1	Individual Plasma Concentrations OF TPOXX BY TREATMENT							
Listing 16.2.6.2	Individual Plasma Pharmacokinetic Parameters of TPOXX by Treatment							
Listing 16.2.7.1	Adverse Events							
Listing 16.2.7.2	Serious Adverse Events							
Listing 16.2.7.3	Adverse Events Leading to Early Study Discontinuation							
Listing 16.2.7.4	Treatment-Related Adverse Events							
Listing 16.2.8.1	Hematology Laboratory Test Results							
Listing 16.2.8.2	Abnormal Laboratory Results (Toxicity Grade of at least 1) in Hematology							
Listing 16.2.8.3	Serum Chemistry Laboratory Test Results							

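### The ECG summary sentence in SAP 9.5 covers only baseline values, contradicting Protocol 7.3.2, SAP Section 4 and the title of SAP Table 14.3.6; it is probably a drafting slip and should be corrected

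*Combined protocol and SAP*

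**What the plan says.** The ECG summary is described in four places.

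- **SAP 9.5** has one sentence on it: "Actual values at baseline for numeric ECG data will be summarized by visit and treatment for subjects in the safety population". The section mentions neither post-dose values nor change from baseline. Its only other ECG output is a listing of all ECG data.
- **Protocol 7.3.2**, with the same text in the synopsis: "Actual values and changes from baseline for clinical laboratory test results, vital sign measurements, and 12-lead ECG results will be summarized by treatment", and this at each time point.
- **SAP Section 4** gives a general rule that safety outcomes, ECG measures among them, are summarised by treatment.
- **SAP Section 14** lists Table 14.3.6, for the safety population, under a title that begins "Summary and Change from Baseline in Electrocardiogram".

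SAP Section 4 also fixes the baseline: "Baseline will be defined as the day the subject checks in (Day -1) before the first dose of study drug administration". Protocol 6.2.5 sets the on-treatment recordings: "On Day 1 of each period, an ECG will be recorded 4 hours after study drug administration". The schedule in SAP Section 13 agrees.

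**The concern.** The sentence in 9.5 is the SAP's specific rule for ECG data, and a programmer would normally let it govern over a general rule or a table title. Followed as written, it gives a table of pre-dose values and no summary of QTcF, QT, PR, RR, QRS or heart rate after TPOXX alone or with any binder.

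ECG is a named safety assessment in Protocol 6.2 and serves the secondary objective of safety and tolerability. The SAP does not declare a departure from the protocol here. The mismatch therefore looks unintended, and the SAP leaves it unresolved.

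**Working it through.** No figure in the plan needs reproducing. The check compares the texts and counts the scheduled ECGs.

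**1. Can the sentence be carried out?** All four sequences begin with Treatment A in Period 1, and baseline is Day -1 before the first dose. Each subject therefore has one baseline, which precedes all five treatments. A baseline summary by visit has a single visit. A baseline summary by treatment repeats the same values in every treatment column, except for subjects who missed a treatment. Neither split carries information.

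**2. Does it agree with the other texts?**

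- Protocol 7.3.2 requires observed values and changes, by treatment, at each time point. The 9.5 sentence gives no changes and no post-dose time points.
- A change-from-baseline table, which is what the title of Table 14.3.6 describes, cannot be filled from baseline values alone.
- The rule in SAP Section 4 of summarising ECG measures by treatment has no useful content if only pre-treatment values are shown.
- SAP 9.2 (laboratory tests) and 9.3 (vital signs) both give actual results and change from baseline at each time point. ECG is the exception.

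**3. How many recordings does the literal text leave out?** The inputs are the ECG rows of the schedules of events (Protocol Tables 9-1 and 9-2; SAP Section 13), 44 subjects enrolled (Protocol Section 3) and at least 36 completing (Protocol 7.1).

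- ECGs per subject: 1 screening + 1 on Day -1 + 5 at 4 hours post-dose (Days 1, 8, 15, 22 and 29) + 1 on Day 36 = 8.
- Inside the 9.5 summary: 1 per subject, so 44 (or 36).
- Post-dose, outside it: 44 × 5 = 220; for 36 completers, 36 × 5 = 180.
- Post-dose plus Day 36, outside it: 44 × 6 = 264; for 36 completers, 36 × 6 = 216.

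**4. Where would Day 36 go?** Protocol 7.3.2 asks for summaries by treatment, but the Day 36 ECG follows no new dose. SAP 9.1 assigns an adverse event to the most recent treatment received; no such rule is stated for ECGs. If that rule were borrowed, Day 36 values would fall under the Period 5 treatment: E, D, C or B, depending on the sequence. With 1:1:1:1 allocation and full completion, that is 44 / 4 = 11 subjects each under B, C, D and E, and none under A. The choice changes the table, so it has to be written down.

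**The case against.** The strongest reply is that nobody would misread this. Protocol 7.3.2, SAP Section 4 and Table 14.3.6 all point to on-treatment values. The odd sentence out makes no sense read literally, and the phrase about visit and treatment itself suggests that the writer meant values and change from baseline. The SAP is labelled a draft. Every ECG is listed (Listing 16.2.9.2). Individual safety review does not depend on the table either: the investigator judges each ECG for clinical significance, and the medical monitor assesses Grade 3 ECG results.

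Most of this stands, and it limits the point. A reader might infer that the sponsor has dropped the post-dose ECGs from the analysis, or that no ECG statement by treatment could be made from the tables. The documents do not support either inference, because the table index and Section 4 are also part of the plan and the listing is complete. Nor does the QTcF eligibility limit add weight: it applies at screening and Day -1 and says nothing about post-dose summaries. SAP 9.2 and 9.3 are not perfect models, since neither summary sentence mentions treatment and both rely on Section 4 for that.

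What the reply does not remove is the contradiction. A title and a general rule do not set the time points, the change variable or the handling of Day 36. The section that should set them says something else.

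**Conclusion.** The concern holds as an error of wording. The ECG sentence in SAP 9.5 is wrong as written, cannot sensibly be carried out, and conflicts with Protocol 7.3.2, SAP Section 4 and the title of Table 14.3.6. A slip is the likely explanation, though the documents do not say so.

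In size, the summary described in 9.5 covers one ECG per subject and leaves out all five on-treatment ECGs and the Day 36 ECG. The totals of 220 and 180 post-dose recordings assume that every scheduled ECG is obtained, for 44 and 36 subjects respectively, and they ignore replacements. They count recordings missing from that one described summary, not recordings missing from the study report.

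The effect is confined to a descriptive safety table under the secondary objective. The primary pharmacokinetic comparison is untouched.

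**What to change.** Replace the sentence in SAP 9.5 with one stating that numeric ECG parameters, QTcF included, will be summarised for the safety population as observed values and as changes from the Day -1 pre-dose baseline, by treatment at each scheduled time point. That follows Protocol 7.3.2 and fits Table 14.3.6.

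Add one sentence on the Day 36 or early-termination ECG, for example under the last treatment received or as a single overall summary. Protocol 7.3.2 does not settle this, so it is a choice for the sponsor to state.

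The cost is two sentences in a SAP still marked as a draft. No new data, no new table number and no protocol amendment are needed. If tables have already been produced from the literal text, SAP Section 11 provides for recording the change in the study report.

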4.4.3 Halting Rules

The medical monitor, investigator, SIGA, and ISM will review all AEs. All AEs determined by the investigator to be severe and possibly, probably, or definitely related to study drug, as well as all clinical assessments, laboratory test results, ECG results, or vital sign measurements that meet Grade 3 criteria on the DAIDS AE Grading Table⁵ will be assessed by the medical monitor, who will make a recommendation as to whether or not halting of the study should occur. At the discretion of the medical monitor, depending on the assessment of the severity of the event, the recommendation to halt the study may be made after consultation with the investigator, SIGA, and the ISM.

The study will be temporarily halted (no new enrollments and no further study drug administration) by the investigator and the medical monitor, SIGA, and the ISM will be promptly notified according to the following criteria:

- One subject experiences a Grade 4 AE assessed as possibly, probably, or definitely related to study drug.
- There is a subject death assessed as possibly, probably, or definitely related to study drug.
- One subject experiences a seizure assessed as possibly, probably, or definitely related to study drug.
- Two or more subjects experience the same or similar SAEs that are possibly, probably, or definitely related to the study drug.
- Three or more subjects experience the same or similar AEs that are Grade 3 or above and are possibly, probably, or definitely related to the study drug.

Study enrollment and study drug administration would resume if review of the AEs that caused the halt resulted in a recommendation to permit further continuation. In such an instance, SIGA, with participation by the investigator and the medical monitor, would consult with the ISM to conduct the review of all AEs that meet the criteria for halting the study. The study would remain suspended until the events were reviewed by the ISM and a recommendation was made as to whether the study should be continued or stopped. This constitutes a minimum criterion, and the decision to halt the study may be made based on any other criteria that, in the judgment of the investigator, with agreement of the medical monitor

and ISM, indicate a potentially serious safety concern. The investigator will advise SIGA immediately if any of the halting rules are met.

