9.2 Clinical Laboratory Evaluations

The following laboratory tests will be performed:

Hematology Hematocrit, hemoglobin, mean corpuscular hemoglobin, mean

corpuscular hemoglobin concentration, total and differential leukocyte count (basophils, eosinophils, lymphocytes, monocytes, neutrophils), mean corpuscular volume, platelet count, red blood cell count, and red

cell distribution width

Serum Chemistry Alanine aminotransferase, albumin, alkaline phosphatase, anion gap,

aspartate aminotransferase, bilirubin (total), blood urea nitrogen, calcium, carbon dioxide, chloride, creatinine clearance (calculated^a), gamma-glutamyltransferase, globulin, glucose, lactate dehydrogenase,

phosphorus, potassium, sodium, total protein, and uric acid

Urinalysis Appearance, bilirubin, blood, color, glucose, ketones, leukocyte

esterase, microscopy (performed if dipstick is $\geq 1+$; includes bacteria, casts, crystals, epithelial cells, red blood cells, and white blood cells), nitrites, pH, protein, specific gravity, turbidity, and urobilinogen

(a) Creatinine clearance will be calculated using the Cockcroft-Gault formula:

Creatinine clearance (mLmin /) =
$$\frac{[140 - age(years] \ x \ weight(kg)}{72 \ x \ serum \ creatine} \{x \ 0.85 \ if \ female\}$$

The hematology, serum chemistry, and urinalysis tests will be performed at the timepoints indicated in the schedule of assessments (schedules of assessments can be found in Section 13). Glycosylated hemoglobin A1c and a fasting lipid panel including cholesterol (total, high-density lipoprotein, calculated low-density lipoprotein, and triglycerides) will be performed at screening.

Note: All lab parameters will be graded according to the Division of Acquired Immune Deficiency Syndrome (DAIDS)³ toxicity grading scale and will be adjusted according to local laboratory reference ranges.

Serum pregnancy test (β human chorionic gonadotropin) for women of childbearing potential will be performed at screening. A urine pregnancy test will be performed at check-in on Day -1. A positive urine pregnancy test will be verified with a follow-up serum pregnancy test.

A serum follicle-stimulating hormone test for postmenopausal women will be performed at screening.

Human immunodeficiency virus (type 1 and 2) antibodies, hepatitis B surface antigen, and hepatitis C virus antibody will be assessed at screening only.

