All clinical laboratory test results will be presented in the data listings. Laboratory values that are outside of the normal reference range will be flagged in the data listings.

Actual results and change from baseline for hematology, serum chemistry and urinalysis at each time point will be summarized for the safety population. Shift from baseline in terms of low/normal/high for hematology and serum chemistry tests, and in terms of normal/abnormal for urinalysis tests will be summarized for the safety population. Abnormal laboratory values for hematology, serum chemistry and urinalysis, defined as any laboratory value with a toxicity grade of 1 or above, will be presented in a listing.

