Listing 16.2.8.4	Abnormal Laboratory Results (Toxicity Grade of at least $oldsymbol{1}$) in Chemistry							

Listing 16.2.8.5	Jrinalysis Laboratory Test Results						
Listing 16.2.8.6	Abnormal Laboratory Results (Toxicity Grade of at least 1) in Urinalysis						
Listing 16.2.9.1	Vital Sign Measurements						
Listing 16.2.9.2	Electrocardiograms						
Listing 16.2.9.3	Physical Examinations						
Listing 16.2.9.4	Follow-Up Call						

16. Appendix

PARAMETER	GRADE 1 MILD	GRADE 2 MODERATE	GRADE 3 SEVERE	GRADE 4 POTENTIALLY LIFE- THREATENING
Albumin, Low (g/dL; g/L)	3.0 to < LLN 30 to < LLN	≥ 2.0 to < 3.0 ≥ 20 to < 30	≥ 2.0 to < 3.0 ≥ 20 to < 30	NA
Alkaline Phosphatase, High	1.25 to < 2.5 x ULN	2.5 to < 5.0 x ULN	5.0 to < 10.0 x ULN	≥ 10.0 x ULN
ALT or SGPT, High *Report only one	1.25 to < 2.5 x ULN	2.5 to < 5.0 x ULN	5.0 to < 10.0 x ULN	≥ 10.0 x ULN
AST or SGOT, High *Report only one	1.25 to < 2.5 x ULN	2.5 to < 5.0 x ULN	5.0 to < 10.0 x ULN	≥ 10.0 x ULN
Bilirubin	•	•		•
Direct Bilirubin ¹ , High > 28 days of age	NA	NA	> ULN with other signs and symptoms of hepatotoxicity.	ULN with lifethreatening consequences (e.g., signs and symptoms of liver failure)
Total Bilirubin ¹ , High > 28 days of age	1.1 to < 1.6 x ULN	1.6 to < 2.6 x ULN	2.6 to < 5.0 x ULN	≥ 5.0 x ULN
Calcium, High (mg/dL; mmol/L) ≥7 days of age	10.6 to < 11.5 2.65 to < 2.88	11.5 to < 12.5 2.88 to < 3.13	12.5 to < 13.5 3.13 to < 3.38	≥ 13.5 ≥ 3.38
Calcium, Low (mg/dL; mmol/L) ≥ 7 days of age	7.8 to < 8.4 1.95 to < 2.10	7.0 to < 7.8 1.75 to < 1.95	6.1 to < 7.0 1.53 to < 1.75	< 6.1 < 1.53

Calcium (Ionized), Low (mg/dL; mmol/L)	< LLN to 4.0 < LLN to 1.0	3.6 to < 4.0 0.9 to < 1.0	3.2 to < 3.6 0.8 to < 0.9	< 3.2 < 0.8
Cholesterol, Fasting, High ≥ 18 years of age	200 to < 240 5.18 to < 6.19	240 to < 300 6.19 to < 7.77	≥ 300 ≥ 7.77	NA
LDL, Fasting, High ≥ 18 years of age	130 to < 160 3.37 to < 4.12	160 to < 190 4.12 to < 4.90	≥ 190 ≥ 4.90	NA
Triglycerides, Fasting, High	150 to 300 1.71 to 3.42	>300 to 500 >3.42 to 5.7	>500 to < 1,000 >5.7 to 11.4	> 1,000 > 11.4
Creatine Kinase, High	3 to < 6 x ULN	6 to < 10x ULN	10 to < 20 x ULN	≥ 20 x ULN
Creatinine, High *Report only one	1.1 to 1.3 x ULN	> 1.3 to 1.8 x ULN OR Increase to 1.3 to < 1.5 x participant's baseline	> 1.8 to < 3.5 x ULN OR Increase to 1.5 to < 2.0 x participant's baseline	\geqslant 3.5 x ULN OR Increase of \geqslant 2.0 x participant's baseline

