Creatinine Clearance ² or eGFR, Low *Report only one	NA	< 90 to 60 ml/min or ml/min/1.73 m2 OR 10 to < 30% decrease from participant's baseline	< 60 to 30 ml/min or ml/min/1.73 m2 OR 30 to < 50% decrease from participant's baseline	< 30 ml/min or ml/min/1.73 m2 OR ≥ 50% decrease from participant's baseline or dialysis needed
Glucose (mg/dL; mmol/L) Fasting, High	110 to 125 6.11 to < 6.95	> 125 to 250 6.95 to < 13.89	> 250 to 500 13.89 to < 27.75	≥ 500 ≥ 27.75
Nonfasting, High	116 to 160 6.44 to < 8.89	> 160 to 250 8.89 to < 13.89	> 250 to 500 13.89 to < 27.75	≥ 500 ≥ 27.75
Glucose, Low (mg/dL; mmol/L) ≥ 1 month of age	55 to 64 3.05 to <3.55	40 to < 55 2.22 to < 3.05	30 to < 40 1.67 to < 2.22	< 30 < 1.67

Hemoglobin³, Low (g/dL; mmol/L) ¹⁷ ≥ 13 years of age (male only)	10.0 to 10.9	9.0 to < 10.0	7.0 to < 9.0	< 7.0
	6.19 to 6.76	5.57 to < 6.19	4.34 to < 5.57	< 4.34
≥ 13 years of age	9.5 to 10.4	8.5 to < 9.5	6.5 to < 8.5	< 6.5
(female only)	5.88 to 6.48	5.25 to < 5.88	4.03 to < 5.25	< 4.03
Potassium, High	5.6 to < 6.0	6.0 to < 6.5	6.5 to < 7.0	≥ 7.0
(mEq/L; mmol/L)	5.6 to < 6.0	6.0 to < 6.5	6.5 to < 7.0	≥ 7.0
Potassium, Low	3.0 to < 3.4	2.5 to < 3.0	2.0 to < 2.5	< 2.0
(mEq/L; mmol/L)	3.0 to < 3.4	2.5 to < 3.0	2.0 to < 2.5	< 2.0
Phosphate, Low (mg/dL; mmol/L) > 14 years of age	2.0 to < LLN 0.65 to < LLN	1.4 to < 2.0 0.45 to < 0.65	1.0 to < 1.4 0.32 to < 0.45	< 1.0 < 0.32
Sodium, High	146 to < 150	150 to < 154	154 to < 160	≥ 160
(mEq/L; mmol/L)	146 to < 150	150 to < 154	154 to < 160	≥ 160
Sodium, Low	130 to < 135	125 to < 130	121 to < 125	≤ 120
(mEq/L; mmol/L)	130 to < 135	125 to < 130	121 to < 125	≤ 120
Urate (umol/L), High (umol/L; μmol/L)	>1 x ULN >1 x ULN	NA	NA	NA
Eosinophils (10^9/L; /mm3)	>1 x ULN >1 x baseval	NA	NA	NA
Hemoglobin³, Low (g/dL; mmol/L) ⁴ ≥ 13 years of age (male only)	10.0 to 10.9	9.0 to < 10.0	7.0 to < 9.0	< 7.0
	6.19 to 6.76	5.57 to < 6.19	4.34 to < 5.57	< 4.34
≥ 13 years of age (female only)	9.5 to 10.4	8.5 to < 9.5	6.5 to < 8.5	< 6.5
	5.88 to 6.48	5.25 to < 5.88	4.03 to < 5.25	< 4.03

Absolute Lymphocyte Count, Low (cell/mm3; cells/L) > 5 years of age (not HIV infected)	600 to < 650 0.600 x 109 to < 0.650 x 109	500 to < 600 0.500 x 109 to < 0.600 x 109	350 to < 500 0.350 x 109 to < 0.500 x 109	< 350 < 0.350 x 109
Absolute Neutrophil Count (ANC), Low (cells/mm3; cells/L) > 7 days of age	800 to 1,000 0.800 x 109 to 1.000 x 109	600 to 799 0.600 x 109 to 0.799 x 109	400 to 599 0.400 x 109 to 0.599 x 109	< 400 < 0.400 x 109

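### The SAP grading table gives albumin Grades 2 and 3 the same range and no grade below 2.0 g/dL, so the lowest values would miss the grade-based chemistry listing (minor)

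*Combined protocol and SAP*

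**What the plan says.** The SAP's Section 16 Appendix sets out a four-grade laboratory table. For low albumin, Grade 1 is "3.0 to < LLN 30 to < LLN" (g/dL, then g/L). The Grade 2, Grade 3 and Grade 4 cells follow as "≥ 2.0 to < 3.0 ≥ 20 to < 30 ≥ 2.0 to < 3.0 ≥ 20 to < 30 NA".

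Albumin is a study analyte: the serum chemistry panel in SAP Section 9.2 begins "Alanine aminotransferase, albumin, alkaline phosphatase, anion gap". The same section says that laboratory parameters are graded on the DAIDS scale, adjusted to local reference ranges. It sends abnormal hematology, chemistry and urinalysis values, "defined as any laboratory value with a toxicity grade of 1 or above, will be presented in a listing", to Listings 16.2.8.2, 16.2.8.4 and 16.2.8.6 of the SAP's Section 15 index.

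Section 9.2 also plans outputs that do not use the grade: full listings of every result with out-of-range values flagged, and shift tables (low/normal/high for hematology and chemistry, normal/abnormal for urinalysis).

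In the protocol, Section 4.4.3 refers to the medical monitor "laboratory test results, ECG results, or vital sign measurements that meet Grade 3 criteria on the DAIDS AE Grading Table". Section 4.4.1 (withdrawal) and Section 6.2.1.5 (severity) cite DAIDS Version 2.1, July 2017.

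**The concern.** A grading table should give each value below the lower limit of normal (LLN) exactly one grade, and the grade should rise as the value worsens. The albumin row does neither. One band carries two grades, and the band beneath it carries none. Because entry to the abnormal chemistry listing depends on having a grade, the lowest albumin values would be left out of a listing that milder ones enter. Those listings serve the secondary objective, safety and tolerability.

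**Working it through.** The plan has no computed figure to reproduce here. The check is whether the printed cells cover the albumin range once.

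**Inputs.** The albumin row is from SAP Section 16 and the listing rule (grade at least 1) from SAP Section 9.2. The documents give no LLN for albumin, so I assumed 3.5 g/dL and repeated the check at 3.3 and 3.8.

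**Rule as printed**, for albumin *a* in g/dL: Grade 1 if 3.0 ≤ *a* < LLN; Grade 2 if 2.0 ≤ *a* < 3.0; Grade 3 if 2.0 ≤ *a* < 3.0; no Grade 4. The g/L limits are ten times these (30, 20) and repeat the duplication.

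**Result at LLN 3.5:**

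| Albumin (g/dL) | Below LLN? | Grade(s) met | Enters Listing 16.2.8.4? |
|---|---|---|---|
| 4.0 | no | none | no |
| 3.4, 3.2, 3.0 | yes | 1 | yes |
| 2.9, 2.5, 2.0 | yes | 2 and 3 | yes |
| 1.9, 1.5, 1.0 | yes | none | no |

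At an LLN of 3.3, the value 3.4 becomes normal; at 3.8, nothing in the table changes. The two lower bands do not depend on the LLN. In the band 2.0 to <3.0 the grade reported depends on the program: first match gives Grade 2, highest match gives Grade 3.

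**Comparison with other rows of the table.** Low calcium, potassium, phosphate, glucose, male hemoglobin and lymphocytes all step without overlap and end in an open Grade 4 (calcium <6.1 mg/dL, potassium <2.0 mEq/L). Where Grade 4 is NA, as for fasting cholesterol and LDL, Grade 3 is open-ended (≥300 and ≥190). Albumin has Grade 4 NA, but its Grade 3 is closed and repeats Grade 2.

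**Opportunities.** Chemistry is drawn at screening, on Day -1 and Day 2 of each of the five periods, and at Day 36: 1 + 5 + 5 + 1 = 12 scheduled albumin results per subject.

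**Illustration of a repaired row.** If Grade 3 began where Grade 2 ends, following the pattern of the other low rows, each tested value below the LLN would get one grade and enter the listing. This shows the logic only; the actual limit has to come from the DAIDS table, which is not among the documents.

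**Glucose.** The high-glucose Grade 3 and Grade 4 cells, fasting and nonfasting, read "> 250 to 500 13.89 to < 27.75 ≥ 500 ≥ 27.75". Exactly 500 mg/dL satisfies both. The mmol/L limits in the same cells (<27.75 and ≥27.75) do not overlap, so the two units disagree at that one value.

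**The case against.** Several points limit this, and most of them stand.

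*Halting and withdrawal.* A reader might infer that the faulty row changes what the medical monitor reviews or when dosing stops. The documents do not support that. Protocol Sections 4.4.1 and 4.4.3 use the DAIDS table itself, not the SAP appendix.

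*Visibility of severe values.* A reader might infer that an albumin below 2.0 g/dL would go unreported. It would not. It remains in Listing 16.2.8.3 with an out-of-range flag, counts as low in the chemistry shift table (14.3.4.2.2) and enters the change-from-baseline summary (14.3.4.2.1).

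*Effect of the double grade.* The SAP index has no table of laboratory results by toxicity grade. A value of 2.0 to <3.0 enters Listing 16.2.8.4 under either grade, so at most a grade displayed beside it would be ambiguous. Such values are not uniquely graded, which is narrower than saying they are graded wrongly.

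*Source of grades.* SAP Section 9.2 names the DAIDS scale, and nothing says that the appendix overrides it. Programming from DAIDS could avoid the fault. The SAP would still hold an appendix that does not work as a grading rule.

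*PDF reading.* The text of these pages is imperfect, and a merged or duplicated cell cannot be excluded. A merged cell would still leave values below 2.0 without a grade.

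*Urinalysis.* The blank urobilinogen row might suggest that the listing titled "Abnormal Laboratory Results (Toxicity Grade of at least 1) in Urinalysis" must be empty. That is not established. The row lies in a visibly damaged part of the text, and whether DAIDS grades urine tests cannot be settled from these documents.

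**Conclusion.** The point holds as a minor inconsistency in the SAP. As printed, albumin of 2.0 to <3.0 g/dL meets two grades and albumin below 2.0 meets none; programmed literally, the latter would be missing from Listing 16.2.8.4. This rests on two assumptions: that the appendix is used as the grading source, and that the cells read as they do in the issued SAP.

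The practical size is small. The subjects are healthy adults aged 18 to 50, and clinically significant hepatic disease is excluded, so few or none are likely to have albumin below 3.0 g/dL. The PK conclusions do not depend on this table. The glucose overlap concerns one exact value in a population that excludes diabetes.

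**What to change.** - Reconcile the Grade 3 albumin cell, in g/dL and g/L, with the cited DAIDS Version 2.1 table, so that grades do not overlap and every value below the LLN has one grade.
- In the same pass, remove the overlap at exactly 500 mg/dL in the fasting and nonfasting glucose rows.
- State in SAP Section 9.2 whether programming follows the appendix or the DAIDS table if they differ.
- For urinalysis, check that the tests have grades in the grading source. If they do not, base Listing 16.2.8.6 on the normal/abnormal category that Section 9.2 already uses for the shift table.

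The SAP is labelled a draft. The cost is a few cells and sentences and a small change to the grading code; no new data are needed.
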